Assess if the lymphodepletion predictive algorithm developed by UVA coupled with the existing optimization algorithm in radiation treatment planning software predicts the magnitude of lymphocyte depletion in a prospective cohort of patients treated with lung SBRT.	After randomization and completion of treatment planning, the algorithm will predict the decrease in lymphocyte count for each participant (in Arms A and B) at 4 weeks after SBRT. The endpoints are:

	a) the within patient difference in the change from baseline in predicted and observed lymphocyte counts b) the within patient difference in the percent change from baseline in predicted and observed lymphocyte counts
Determine if lymphocyte-sparing SBRT planning (Arm A, investigational) results in less in vivo lymphocyte depletion compared to controls who receive standard SBRT planning (Arm B, control).	Observed changes in lymphocyte count from baseline and 4 weeks after completion of lung SBRT for participants in each arm. Expected lymphocyte nadir time point of 4 weeks following SBRT will be used to estimate both the actual and percentage decreases in lymphocyte counts seen in each arm.
Secondary	
Describe the adverse event profile of participants treated with and without lymphocyte-sparing SBRT planning (Arms A and B).	Frequency, severity, and duration of adverse events according to CTCAE version 5.0
Determine if our lymphodepletion predictive algorithm coupled with the existing optimization algorithm in radiation treatment planning software predicts the magnitude and trajectory of lymphocyte depletion in a prospective cohort of patients treated with lung SBRT.	After randomization and completion of treatment planning, the algorithm will predict the decrease in lymphocyte count for each participant (in Arms A and B) for each follow-up time point (at end of SBRT, and 4 weeks and 6 months after SBRT). The predicted time course of lymphocyte count will be compared with both the actual and percentage decrease in lymphocyte count observed.

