3. OBJECTIVES

3.1 Primary Objectives

3.1.1 Performance of Algorithm to Predict Decrease in Lymphocyte Count Post-SBRT

Determine if the lymphodepletion predictive algorithm developed by UVA coupled with the existing optimization algorithm in radiation treatment planning software predicts the magnitude of lymphocyte depletion in a prospective cohort of patients treated with lung SBRT.

Hypothesis: We hypothesize that our predictive algorithm, which estimates risk of post-SBRT lymphopenia based upon estimation of radiation dose to blood vessels, can accurately predict change in lymphocyte count at 4 weeks following SBRT in a prospective cohort of lung SBRT patients.

Endpoint: After randomization and completion of treatment planning, the algorithm will predict the decrease in lymphocyte count for each participant (in Arms A and B) at 4 weeks after SBRT. The predicted decrease will be compared with the actual decrease in lymphocyte count observed.

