5. STATISTICAL CONSIDERATIONS

Study populations Any participant who initiates either standard or optimized SBRT will be considered evaluable for adverse events. Participants with observed changes in lymphocyte counts at any of the follow-up times will be considered evaluable for the analyses of changes in lymphocyte counts.

Randomization and stratification

[figure not shown]
Participants will be randomized to standard or optimized SBRT in a 1:1 ratio using randomly permuted blocks. Block sizes of 2 or 4 will be randomly chosen with equal probability. The randomization will be stratified by central or peripheral lung lesion (section 4.1.1)

Sample size and power The first aim is to compare the actual and predicted values from the simulations. We will calculate the empirical distribution function of the difference between predicted and actual, both in terms of lymphocyte counts and percent change from pretreatment counts. Current simulation is able to predict to 17% accuracy, with a standard deviation of 15%. The model will be considered an improvement if 80% of the predictions are within 10% of the actual counts or percent changes. With a sample of size 50 evaluable, the one-sample t-test has 95% power, with a one-sided significance level of 5%, for testing whether the mean percent difference is less than 17%, when the true mean is 10%.

The second aim is to compare standard versus optimized SBRT on the basis of the primary outcome, lymphocyte drop at 4 weeks. The sample size was chosen to have sufficient power for comparing the groups using a repeated measures model for comparing the groups. Estimates of effect sizes and variation were based on repeated measures models, with change points at 4 and 12 weeks, fit to retrospective data on lymphocyte drop within 24 weeks following standard SBRT. A spatial-power model was used for the covariance matrix of percentage changes from baseline in lymphocyte counts,

yielding an estimated standard deviation of 10.5 percentage points and a within-subjects correlation estimate of 0.40 for observations taken 1 week apart. The fitted model, overlaid on the individual patient profiles is displayed above.

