With n=25 patients, measured at baseline and 4 and 24 weeks months post radiation, the F-test in the repeated measures model provides 80% power for comparing the mean lymphocyte depletion profile over the follow-up period between the groups. For the power calculation, we assumed that in the optimized dose participants. mean lymphocytes relative to baseline are equal to Δ + $(1-\Delta)\mu(t)$, where $\mu(t)$ is the mean estimated from historical controls at time t = 0, 4, or 24 weeks. With this, $\Delta = 0$ means no effect of the optimization; $\Delta = 1$ means no

lymphocyte depletion with optimized SBRT treatment. *Figure 3* displays the mean profile for Δ = 0.60, a profile for which n = 25 per group yields 80% power for the F-test, with a 2-sided significance level of 5%. For the specific comparison at 4 weeks, a contrast in the repeated measures model has more than 99% power for the assumed profile. We computed power for the comparing the entire trajectory, and not just at 4 weeks, because of the uncertainty in the point at which the maximum drop and the maximum difference between the groups will occur. To allow for 10% dropout, 55 patients will be enrolled in the study.

Analyses. For the first aim, which compares the actual and predicted lymphocyte counts, the empirical distribution function of the differences, both in terms of the lymphocyte count and the percentage change from baseline, will be tabulated. We will assess the proportion of cases in which the predicted values is within 10% of the actual value. In addition to computing the empirical distribution functions, exploratory analyses will assess patient characteristics associated with the magnitude of the deviation between predicted and actual values.

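### The 95% power stated for primary Aim 1 belongs to a mean test outside the planned Aim 1 analyses, and the declared success rule (80% of predictions within 10%) has no stated chance of being met

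*Combined protocol and SAP*

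**What the plan says.** Predicting lymphocyte depletion at 4 weeks is the first of the two primary objectives (Synopsis, Table 1; Section 3.1.1). Table 1 gives two endpoints, the second being "the within patient difference in the percent change from baseline in predicted and observed lymphocyte counts". Section 3.1.1 says only that "The predicted decrease will be compared with the actual decrease in lymphocyte count observed". Neither place sets a numeric criterion.

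The numbers are in Section 5, under sample size and power:

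- Benchmark: "Current simulation is able to predict to 17% accuracy, with a standard deviation of 15" (SD 15%).
- Success rule: "The model will be considered an improvement if 80% of the predictions are within 10% of the actual counts or percent changes".
- Power, for 50 evaluable participants: "the one-sample t-test has 95% power, with a one-sided significance level of 5" (5%), "for testing whether the mean percent difference is less than 17%, when the true mean is 10" (10%).

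The Analyses paragraph of Section 5 plans, for this aim, a tabulated empirical distribution function of the differences and the success proportion: "We will assess the proportion of cases in which the predicted values is within 10% of the actual value". It adds exploratory work on patient characteristics. It lists no t-test, no reference proportion and no confidence interval. For the second aim, Section 5 says "The sample size was chosen to have sufficient power for comparing the groups", so the 95% is a statement about Aim 1 at a sample size fixed elsewhere.

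**The concern.** The success rule concerns a proportion and the power concerns a mean. A reader who sees 95% directly after the rule will take it as the chance that the aim succeeds, and it is not. The test it does describe is not planned, and the rule that is planned has no operating characteristics.

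The rule is also not fully specified. It joins counts and percent changes with an either/or and does not say which decides. For percent change, 10% could be percentage points, since endpoint (b) is a difference between two percent changes, or relative error, since the Analyses text speaks of closeness to the actual value. The documents do not say whether the 17% and 15% figures describe signed or absolute errors. The same data could pass on one reading and fail on another, and the choice could then be made after the results are known.

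At stake is what can be claimed for the algorithm on a primary objective. Participant management and enrolment are not affected.

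**Working it through.** **Inputs (Section 5).** n = 50 evaluable; null mean 17; alternative mean 10; SD 15; one-sided 5%; rule 80% within 10%. I read the rule as an observed proportion of at least 0.80 × 50 = 40 of 50, on one scale.

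**1. The plan's own figure.** Noncentrality = (17 − 10)/(15/√50) = 3.30. With 49 df and one-sided 5%, the noncentral t gives power 0.946; the normal approximation gives 0.951. The stated 95% reproduces.

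**2. The declared rule.** The chance of meeting it is P(X ≥ 40), X ~ Binomial(50, p), where p is the true proportion within 10%:

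| True p | Rule met |
|---|---|
| 70% | 7.9% |
| 75% | 26.2% |
| 80% | 58.4% |
| 85% | 88.0% |
| 87% | 94.7% |

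The chance equals 5% at p = 68.4%. An observed 40/50 has an exact (Clopper-Pearson) 95% interval of 66% to 90%. This step needs no assumption about the shape of the errors.

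**3. Does mean 10, SD 15 determine p?** It does not. Every shape below is my assumption and has that mean and SD. For two-point errors, a share q lies at 10 − 15√((1−q)/q) and the rest at 10 + 15√(q/(1−q)).

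| Error shape | p within 10 | Rule met |
|---|---|---|
| Signed normal | 0.409 | under 0.01% |
| Absolute, gamma | 0.692 | 6.4% |
| Absolute, Weibull | 0.697 | 7.2% |
| Absolute, lognormal | 0.706 | 9.4% |
| Two-point, 80% at 2.5 and 20% at 40 | 0.80 | 58.4% |
| Two-point, 87% at 4.2 and 13% at 48.8 | 0.87 | 94.7% |
| Two-point, 90% at 5 and 10% at 55 | 0.90 | 99.1% |

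**4. Can the two criteria disagree?** They can, in both directions. At mean 10, SD 15, the t-test passes while the rule fails in 79% to 82% of simulated trials for the three smooth absolute-error shapes, in about 30% for the 80/20 two-point shape and in 0% for 87/13 and 90/10. The rule passes while the t-test fails in about 5% of trials for 87/13 and 11% for 90/10.

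**5. False pass at the benchmark (mean 17, SD 15).** The smooth absolute-error shapes put 37% to 41% of errors within 10, and the rule is met with probability 1.4 × 10⁻⁸ or less. An 80/20 two-point shape puts 80% of errors at 17 − 15√(0.2/0.8) = 9.5 and 20% at 17 + 15√(0.8/0.2) = 47; the rule is then met 58% of the time.

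**6. Scale.** Error in percentage points of change = relative error in the count × (observed count/baseline). At assumed observed drops of 20%, 40% and 60%, 10% of the actual count is therefore 10 × 0.8 = 8, 10 × 0.6 = 6 and 10 × 0.4 = 4 percentage points. The readings of 10% are not interchangeable.

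**The case against.** The strongest reply is that this is a pilot, the Aim 1 analysis is largely descriptive, both scales will be tabulated, the sample size came from the group comparison, and no decision to stop, adopt or enrol hangs on the rule. All of that is correct, and it limits the consequence. It does not remove the mismatch: the protocol itself attaches a success rule and a power figure to a primary objective, and the two describe different quantities.

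A reader might infer several stronger points, and the documents do not support them.

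- *The 95% is an error.* It reproduces for the test it names.
- *The rule is almost sure to fail under the plan's own assumptions.* The 6% to 9% pass rates and the roughly 80% disagreement depend on smooth skewed absolute errors. The documents give no error shape, and other shapes with the same mean and SD range from under 0.01% to 99%. The two-point shapes are artificial; they show only that mean and SD leave the answer open.
- *A false pass is negligible.* That holds for the smooth shapes, but not for the 80/20 two-point shape in step 5.
- *Nothing says which criterion governs.* The wording on improvement attaches to the proportion alone, and the Analyses text plans that proportion. The t-test is never called a success criterion.
- *The errors must be absolute.* Section 5 and Table 1 speak only of differences; neither says absolute or signed.

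**Conclusion.** The concern holds in a limited form. Aim 1's only design figure does not describe its declared success rule, and the test it does describe is missing from the planned analyses. An algorithm that truly places 80% of predictions within 10% would meet the rule 58% of the time at n = 50; a 95% chance needs a true proportion of about 87%. These figures rest only on reading the rule as at least 40 of 50 on one scale, and I hold them and the mismatch with high confidence. The shape-based percentages illustrate a range and are not properties of the plan. From the stated mean and SD, neither a high nor a low pass rate, nor a false pass at the benchmark, can be ruled out. The unnamed scale is a separate, smaller gap in the same sentence of Section 5.

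**What to change.** In Section 5:

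1. Keep the 80%-within-10% rule and the 50 evaluable participants. Replace the 95% as Aim 1's design figure with the rule's exact binomial operating characteristics (step 2). Alternatively, label the 95% as the power of a supportive mean test only and list that test under Analyses.
2. State the current algorithm's own proportion within 10%, taken from the data behind the 17% and 15% figures, as the no-improvement reference. If that proportion is about 68% or lower, the false-pass rate of the rule is 5% or less.
3. Name one deciding scale in place of the either/or. Say whether 10% means percentage points or relative error, and whether the 17% and 15% figures are signed or absolute.
4. Report the observed proportion with an exact confidence interval.

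The cost is a few sentences, a few lines of code and a look back at the retrospective data. Sample size does not change. The downside is a less favourable stated figure: 58% if the true proportion is exactly 80%.

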For the second aim, repeated measures models will be used to compare the groups with respect to the percentage drop in lymphocyte counts. The stratification factor will be used as a covariate in the model. Contrasts will be used to compare the groups at specific time points, including the 4 week post-treatment time point, where we anticipate there will be the greatest difference between the standard and optimized SBRT groups. The sample size was based on an assumed spatial power covariance structure, but we will consider other covariance matrices as well, such as random effects models. In exploratory analyses will tabulate local control as well as adverse events (see *section 8*) and estimate differences these between groups. Kaplan–Meier curves will be used to summarize overall survival in each of the standard and optimized SBRT groups.

Quantitative analysis of blood counts and radiation dose to the great vessels

We will collect blood, serum and PBMC at baseline and at end of treatment, weeks 4, and 24 after treatment for all study patients. The reference point for post-treatment blood collection will be the start date of radiation therapy to permit intergroup comparisons between the two study arms. This comparison framework was selected based on our available preliminary data, which

suggests that RT-induced lymphocyte effects occur as early as one week following radiation initiation due to the high radiosensitivity of circulating lymphocytes. We will quantify absolute neutrophils, hemoglobin, platelet, and lymphocyte counts for all patients at these time points and compare the changes between the groups and also compare the lymphocyte count results to what was predicted by the simulation algorithm. We will perform a multivariate analysis to identify the correlation between TRL and mean/integral radiation dose to the great vessels. Since substantial circulating blood is also present in the heart and lungs we will also correlate mean heart and lung dose with TRL. Measurement of the magnitude of lymphocyte depletion and correlation with great vessel, lung, and heart integral dose will be performed and compared to the predicted levels for the simulation algorithm.

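### Does the F-test behind 25 per group need a written null hypothesis, degrees of freedom and visit list before the sample size can be relied on?

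*Combined protocol and SAP*

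**What the plan says.** Under the second aim, Section 5 (Sample size and power) states that "the F-test in the repeated measures model provides 80% power for comparing the mean lymphocyte depletion profile over the follow-up period between the groups". This is for 25 patients per group, and the plan describes them as "measured at baseline and 4 and 24 weeks months post radiation". The words weeks and months both follow the 24. This is a slip, because the next sentence gives the times as 0, 4 and 24 weeks. The assumed profile is Δ = 0.60 applied to a historical mean curve. The covariance is spatial-power, fitted to percentage changes from baseline, "yielding an estimated standard deviation of 10.5 percentage points and a within-subjects correlation estimate of 0.40 for observations taken 1 week apart". The historical model was fitted "with change points at 4 and 12 weeks".

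The plan then adds: "For the specific comparison at 4 weeks, a contrast in the repeated measures model has more than 99% power for the assumed profile". It explains its choice of the global test: "We computed power for the comparing the entire trajectory, and not just at 4 weeks", because the time of the largest drop and of the largest arm difference is uncertain.

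The Analyses paragraph plans repeated measures models with the stratification factor as covariate and contrasts at specific times, week 4 among them. It does not mention the F-test or list the model's visits. A separate paragraph on blood counts says: "We will collect blood, serum and PBMC at baseline and at end of treatment, weeks 4, and 24 after treatment for all study patients". It goes on to quantify "lymphocyte counts for all patients at these time points and compare the changes between the groups". Section 3.2.3 includes the end-of-SBRT count in a secondary comparison between arms.

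**The concern.** A repeated measures model yields several F-tests: a group effect averaged over visits, a group-by-time interaction, or a joint test of the arm differences at the post-baseline visits. These have different degrees of freedom and can have very different power for the same profile. The plan calls its test a comparison of mean profiles and does not say which of these it means. The reference to a two-sided 5% level does not settle it, since sidedness has no meaning for an F-test with more than one numerator degree of freedom.

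The visits add a second question. The calculation uses three times and the study collects four. If the fourth enters the model, a group-by-time test has 3 degrees of freedom instead of 2 and is no longer the test that was powered. Because the plan offers the trajectory comparison as the basis for 25 per group, one could fear that the test run will differ from the test powered, or that it will be picked once the data are in.

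**Working it through.** **Inputs from Section 5.** SD 10.5 points; correlation 0.40 per week apart; 25 per arm; level 5%. **Assumed.** Denominator df 48 (2 × 25 − 2) unless noted, since none is stated; SD 10.5 at every time used. The historical means are not in the text, and the figure that may show them is not available. The 4-week arm difference d4 is therefore solved for, with r as the 24-week difference divided by d4.

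**Standard error.** For one visit, SE = 10.5 × √(2/25) = 2.970, so SE² = 8.82. Correlation between weeks 0 and 4 is 0.40⁴ = 0.0256; between weeks 4 and 24 it is 0.40²⁰, effectively zero.

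**Reproducing the plan's pair.** Take a group-by-time test over 0, 4 and 24 weeks (2 df). It has 80% power when its noncentrality is 10.26. At r = 0.5 the 24-week term drops out and

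λ = d4² / [2 × SE² × (1 − 0.0256)] = 10.26, which gives d4 = 13.28.

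The 4-week contrast for that profile has λ = 13.28² / 8.82 = 20.0 and power 99.2%. Both printed figures are met. The contrast stays at or above 99% for r from about 0.35 to 0.65 and denominator df from 48 to 144.

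**Other candidate tests.**
- Group effect averaged over 0, 4 and 24 weeks (1 df), set to 80%: the contrast has 99.8% power at r = 0 and 99.0% at r = 0.14, so this also fits.
- Week 4 against week 24 (1 df), set to 80%: the contrast has 99.3% at r = 0.10, so this fits too.
- Joint test of the week 4 and week 24 differences (2 df), at the r = 0.5 profile: λ = (13.28² + 6.64²) / 8.82 = 25.0, power 99.4%. Set to 80% instead (df 96), it leaves the contrast at only 60% to 88%, so it is not the test behind the printed pair.

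**Adding the end-of-SBRT count.** Take the group-by-time test at r = 0.5 and d4 = 13.28, with that count placed 1 to 2 weeks after the start of treatment. The arm difference there is not in the documents, so it is varied from none to all of d4.

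| End of SBRT at week | No difference | Linear growth to week 4 | Lowest power | Full d4 |
|---|---|---|---|---|
| 1 | 82.5% | 74.1% | 73.5% | 96.2% |
| 1.5 | 85.7% | 73.7% | 73.5% | 92% |
| 2 | 88.7% | 73.5% | 73.5% | 88.7% |

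Allowing r from 0.35 to 0.65 and df up to 192, the range is 73.5% to about 97%. Power is U-shaped in the unknown difference, and linear growth lies almost at the bottom. The 29 per group that would restore 80% (80.8% to 81.3%) belongs to that near-worst case. For the 1-df average over visits, the same linear assumption gives about 76% to 92%.

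**The 4-week contrast alone.** With 25 per group it has 80% power at 8.5 points, 90% at 9.8 and 99% at 13.0. None of these depends on which F-test is meant or on whether the fourth visit is in the model.

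**The case for a change.** The strongest case for a change starts from the outcome. Two readings that reproduce the printed pair, the three-time interaction and the three-time average, treat baseline as a response with its own variance. Yet the planned outcome is percentage drop, which is zero at baseline for everyone. A statistician following the Analyses paragraph could reasonably run a joint test of the post-baseline differences, or add the end-of-SBRT visit, and neither would be the test that was powered. Two sentences would settle it.

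Part of this stands. The formal null hypothesis, the degrees of freedom and the analysis visit list are not written down, and stating them would be good practice. The harm does not follow. The joint post-baseline test has more power than the printed 80% for the reconstructed profile (99.4%), so moving to it does not weaken the trial. Adding the visit may raise or lower power. The figures of about 74% and 29 per group also give baseline an SD of 10.5, although Section 5 ties that SD to changes from baseline, so they cannot carry a case for enlarging a pilot.

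The worry about choosing the test after seeing the data has limited reach. Sections 3.1.2 and 5 fix the primary outcome at 4 weeks, and the Analyses paragraph names the 4-week contrast. The comparison that includes the end of SBRT is secondary. The paragraph that compares all time points also covers neutrophils, hemoglobin and platelets and does not refer to the F-test.

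**Conclusion.** No change to the plan is called for. The visits of the power calculation are stated and the hypothesis is given in words; its formal version, the degrees of freedom and the visit list of the analysis model are left to the analyst. No printed figure is shown to be wrong: 80% and more than 99% occur together under an ordinary group-by-time test at a 4-week difference of about 13.3 points. Leaving one collected visit out of a power calculation is not an error in itself. It would matter only if that visit entered the F-test, and the effect would then be somewhere between a loss of about 6.5 points and a gain of about 17. The primary 4-week comparison is unaffected, and 25 per group is not shown to be too small for it.

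This rests on SD 10.5 at every time used, the stated spatial-power correlation, denominator df between 48 and 192, and, for the four-visit figures, an assumed end-of-SBRT difference between none and the full 4-week difference.

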9. STUDY CALENDAR OF ASSESSMENTS

Procedures	Screening/Baseline ¹	SBRT (5 clinic days)	Completion of SBRT ⁵	4 weeks +/-2 weeks following SBRT	3 months +/-2 weeks following SBRT	6 to 9 months following SBRT	Overall Survival (every 6 months for one year and then annually, by phone or medical record review)
Informed consent	X						
Demographics	Х						
Medical history	Х						
Randomization	X^7						
Concomitant medication review	X8		X			X	
Physical exam	Х		Х		Х		
COVID-19 Questions	Х		Х		Х	Χ	
Vital signs	Х		Х		Х		
Height	X (last recorded for standard clinical care)						
Weight	Х		X ⁶			X ⁶	
Performance status	X		X			Х	
Serum or urine pregnancy test (Women of Childbearing Potential Only)	Х						
0 110 1 1 (00)							
Overall Survival (OS)							Х
Hematology- CBC with Diff	X		X ⁴	Х		Х	X ³
Research Blood	X ²			Х			
Planning/Chest CT	X (w/in 8						
scan with contrast	wks of SBRT) ⁷				X ⁶		
Review of Medical Record (see section 8.1.4)	Х		Х		Х	Х	Х
Adverse event review and evaluation	X					X	
SBRT		Х					

¹ All screening procedures should occur up to 1 month prior to registration unless otherwise specified

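### The covariance structure for the Aim 2 repeated measures model is left open, and the single-variance forms the plan points to can misstate the standard error of the primary week-4 comparison in either direction

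*Combined protocol and SAP*

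**What the plan says.** Section 5 (Sample size and power) compares the arms "on the basis of the primary outcome, lymphocyte drop at 4 weeks". For planning, "A spatial-power model was used for the covariance matrix of percentage changes from baseline in lymphocyte counts". That fit, to retrospective data, gave a single SD of 10.5 points and a correlation of 0.40 between counts one week apart. The power calculation takes patients as "measured at baseline and 4 and 24 weeks months post radiation". It reports 80% power for an F-test of the whole profile and more than 99% for the week-4 contrast, with 25 patients per arm, Δ = 0.60 and a two-sided 5% level.

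Section 5 (Analyses) then specifies repeated measures models of the percentage drop, the stratification factor as covariate, and contrasts at specific times including week 4. On the covariance it says only that the sample size used "an assumed spatial power covariance structure, but we will consider other covariance matrices as well, such as random effects models". It names no primary structure, selection rule, visit-specific variances, robust standard error or degrees-of-freedom method.

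The same section plans blood collection "at baseline and at end of treatment, weeks 4, and 24 after treatment for all study patients". The Section 9 calendar sets the end-of-treatment count within 3 days after SBRT, the next at 4 weeks ±2 weeks, and the late one at "6 to 9 months following SBRT".

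**The concern.** In a repeated measures model the standard error of the week-4 contrast comes from the fitted covariance matrix, not from the week-4 data alone. Spatial power has one variance parameter, and so does the marginal variance of a random-intercept model. Under either, the week-4 error bar is built from an average of the spread at all visits.

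The visits are unlike one another: one immediately after treatment, one at the expected nadir (Section 3.1.2), and one in a three-month window half a year or more later. Nothing in the documents supports equal spread across them. If week 4 is the noisiest visit, the pooled error bar is too short and the false-positive rate rises. If the late visit is the noisiest, it is too long and power is lost. With no structure named, the choice would also fall after the data are in hand.

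**Working it through.** **Inputs from Section 5.** SD 10.5 points; correlation 0.40 at one week; 25 per arm; Δ = 0.60; two-sided 5%. **Assumed, because the documents give no values:** SDs by visit, and the true correlation between visits.

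**1. The plan's own figures.** The standard error of an arm difference at one visit is 10.5 × √(2/25) = 2.97 points. The historical mean profile appears only in a figure that is not available, so the stated powers cannot be reproduced. Working backwards, 99% power at week 4 needs a difference of about 12.7 to 13.0 points. At Δ = 0.60 that is a control drop of 12.7/0.60 = 21.2% to 13.0/0.60 = 21.7%, which is plausible but cannot be checked.

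**2. The planning covariance.** One SD applies at every visit, and the correlation between weeks 4 and 24 is 0.40^20 = 1.1 × 10⁻⁸. This describes the sample-size model. Nothing says the correlation will be held at 0.40 in the analysis.

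**3. Two visits, closed form.** Let k = SD(24)/SD(4). A single variance estimates the average, so the ratio of used to true week-4 standard error is √((1 + k²)/2). The true two-sided error is 2Φ(−1.96 × ratio).

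| k | ratio | true error |
|---|---|---|
| 0.67 | 0.850 | 9.6% |
| 0.80 | 0.906 | 7.6% |
| 1 | 1.000 | 5.0% |
| 1.25 | 1.132 | 2.7% |
| 1.5 | 1.275 | 1.3% |

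**4. Three visits.** The same approximation, with assumed SDs at end of SBRT / week 4 / month 6:

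- 7/12/10: pooled SD √((49 + 144 + 100)/3) = 9.88; ratio 9.88/12 = 0.824; error 2Φ(−1.614) = 10.6%.
- 7/10.5/10.5: pooled SD √((49 + 110.25 + 110.25)/3) = 9.48; ratio 0.903; error 2Φ(−1.769) = 7.7%.
- 10.5/10.5/15: pooled SD √((110.25 + 110.25 + 225)/3) = 12.19; ratio 1.161; error 2Φ(−2.275) = 2.3%.

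REML simulations with 25 per arm, true correlation 0.4 at all lags and the correlation parameter estimated gave:

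| SDs | spatial power | random intercept |
|---|---|---|
| 7/12/10 | 9.2–10.8% | 10.0% |
| 7/10.5/10.5 | 6.4–6.8% | 7.2% |
| 10.5/10.5/15 | 1.7–2.2% | 2.3% |
| equal | about 5% | 4.7% |

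The ranges are across separate sets of runs. Taking the better-fitting of the two structures gave 10.0%, 7.1%, 2.3% and 4.6%, so choosing between them does not help. Milder differences matter less: 4.3% for 9.5/10.5/11.5 and 6.2% for 9.5/11.5/10.5.

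**5. Cost in the conservative direction.** For 10.5/10.5/15 and a true 8.5-point difference (8.5/2.97 = 2.86), large-sample power is Φ(2.86 − 2.275) = 72%, against Φ(2.86 − 1.96) = 82% with the correct standard error. At 12.7 points (12.7/2.97 = 4.28) it is still Φ(4.28 − 2.275) = 98%.

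**6. Unstructured covariance.** Week-4 error was 4.7–5.8% across all settings examined. The joint test was 4.9–5.2% with a small-sample correction. Without one it was 5.2–5.6% with two visits and 5.7–6.0% with three.

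**The case against.** The strongest reply is that the plan commits to no wrong structure. Spatial power is introduced as the sample-size assumption, other matrices are expressly allowed, and random-slope models, whose variances do change over time, fit the wording. That stands: a reader might infer that spatial power is the declared analysis default, and Section 5 does not say so.

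Three further readings are tempting and not supported.

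- **That the analysis treats week 4 and month 6 as independent.** The 0.40 comes from retrospective data and would normally be re-estimated. With two post-baseline visits the fitted correlation tracks the truth (0.29, 0.49 and 0.67 for true values of 0.3, 0.5 and 0.7). With three it is too low (about 0.00, 0.01 and 0.15). Even so, at equal SDs the week-4 error stays at 4.0–5.3%. Correlation alone does not break this test.
- **That the trajectory test fails too.** A joint F-test of post-baseline arm differences ran at 4.3–7.1% across all scenarios. A test of the arm effect averaged over visits would be more sensitive, but the plan names no such test.
- **That a constant baseline row enters the model.** The baseline time appears where the assumed mean curve is defined (μ(t) "is the mean estimated from historical controls at time t = 0, 4, or 24 weeks"). The modelled response is a percentage change or drop from baseline, and no sentence enters baseline as a response.

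It can also be said that a continuous-time structure uses actual draw dates, whereas an unstructured matrix treats the windows as fixed visits. That is a real trade-off. What the reply leaves unanswered is that the primary contrast has no named covariance, and that spatial power and the simplest random effects model share the same weakness.

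**Conclusion.** The point holds in a conditional form. The primary week-4 test is not assured its 5% level, because its covariance is unspecified and the single-variance forms depend on equal spread across visits. Under the assumed SDs, true error runs from about 1–2% when month 6 is noisier to about 10% when week 4 is noisiest, and is about 5% when SDs are equal.

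A reader might go further and say that the test does not hold 5%. The documents do not support that: they give one SD and none by visit, so neither direction nor size can be settled from them. That uncertainty is itself the reason to name a structure that does not depend on equal variances. This is an inexpensive improvement to the primary randomised comparison in a pilot of 50 evaluable patients, not a demonstrated error in its result.

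**What to change.** State in Section 5 (Analyses) that the primary Aim 2 model:

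- takes as responses the post-baseline visits only (end of SBRT, 4 weeks, 6 months);
- has arm-by-visit means and the stratification factor;
- uses an unstructured covariance with Kenward-Roger degrees of freedom;
- gives the primary result as the week-4 contrast.

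Spatial power and random effects models are then used only if this model does not converge, or as sensitivity analyses.

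The cost is one or two sentences of text and a few degrees of freedom: three visits need six covariance parameters, which 50 patients can support. The model treats draws within 4 weeks ±2 weeks and within 6 to 9 months as nominal visits, and the plan should say so. A continuous-time structure using actual draw dates can serve as the sensitivity analysis on that point.
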